## 5 STUDY DESIGN

We plan a pilot randomized controlled trial randomizing surgeons to either intervention (direct feedback) or control (no direct feedback) arms. Surgeons frequently performing specific elective general, gynecologic, orthopedic, and neurological surgeries at VUMC will be identified during a 30-day study lead-in period. Then, patients aged at least 18 years undergoing these surgeries at VUMC during study days 1-60 will be contacted by telephone 14 days postoperatively (study days 15-74) and asked to perform an opioid pill count; they will also be asked about opioid refills, satisfaction with analgesia, emergency room visits or hospitalizations for pain, and opioid misuse. The electronic medical record will be also queried for the size of the initial postoperative opioid prescription as well as evidence of any refills for each enrolled subject. We anticipate successfully contacting 5 patients per day for a total of 300 patients in this initial phase. We plan to consent patients electronically at the time of the telephone contact as consenting patients immediately after surgery may influence their subsequent opioid consumption.

Surgeons will be consented without overt discussion of the nudge intervention. Following the first block of surgeries and associated patient follow-up (study days 1-74), data will be analyzed and then surgeons will be randomized in a 1:1 ratio to the intervention or control arms. Randomization will be stratified by both surgical specialty and by mean opioid prescription size during the initial block of surgeries. After study day 97, surgeons in the intervention arm will be provided procedure-specific direct feedback on opioid prescribing and consumption for their patients who had surgery during days 1-60.

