After this intervention, we will assess pre-post change in opioid prescription size (measured in oral morphine equivalents) from baseline between the two groups for surgeries performed during days 108-167. That is, mean size of post-intervention prescriptions (from electronic medical record queries) will be compared with mean pre-intervention prescription size by the same surgeon for the same procedure in order to calculate change from baseline. Primary outcomes are measures of study feasibility and acceptability given that this is a pilot study. The main exploratory outcome will be mean percentage change in procedure-specific prescription size. We will then compare mean per-surgeon percentage change in prescription size between the direct feedback and no-direct-feedback groups. Multiple regression analyses adjusting for case type and surgical specialty will also be employed to permit more granular examination of the targeted changes. To evaluate other exploratory outcomes, we will contact patients undergoing post-intervention surgeries (during days 108-167) 14 days postoperatively (days 122-181) to assess pre-post changes in patient opioid consumption, satisfaction with analgesia, medical visits for pain, opioid refills, and opioid misuse. We again anticipate contacting 5 patients per day for a total of 300 patients in this second phase.

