### 6.3 Study Enrollment Procedures

During the 30-day lead-in period, study *surgeon* participants will be identified through VUMC EMR queries of historical and booked case numbers for the specific procedures listed in section 4.1, above. Given the nature of the planned behavioral nudging intervention, it is not feasible for full consent to be obtained prospectively from surgeon participants as this would very likely affect prescribing behavior in both the Intervention and Control Arms due to the Hawthorne effect. Consequently, we plan to request permission from the VUMC Institutional Review Board to utilize deception for *surgeon* participants, who will be asked to consent for participation in a study giving them information about their patients' opioid consumption (surgeons will be debriefed fully on study purposes upon completion of the study). Surgeon participants will be prospectively selected in a participant log kept by study staff. Surgeons will be randomized on a 1:1 basis to either the Intervention or Control Arms prior to administration of the nudge intervention. Enrolled surgeons must complete a minimum 3 listed cases during the initial 60-day study period (study days #1-60) to be eligible for randomization.

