## 7 STUDY INTERVENTIONS

### 7.1 Interventions, Administration, and Duration

The one-time contact of *patient* participants will take place on postoperative day 14 (or no later than postoperative day 19) for the initial contact group. After verifying eligibility and documenting consent, patients will be asked to obtain their prescribed opioid pill bottle and conduct a pill count. If the patient consumed the entirety of the prescription and disposed of the bottle, this will be documented. If the patient does not have their pill bottle readily available, arrangements will be made to follow up with the patient by telephone or secure electronic messaging later to complete this aspect of the query. Patient participants will also be asked to answer several questions related to our exploratory outcomes:

- Overall satisfaction with postoperative analgesia (numeric rating scale)
- To select from the following answers: “I received a) too many opioid pills, b) the right amount of opioid pills, c) too few opioid pills.”
- Whether patient required any medical visits primarily due to postoperative pain (office visits, emergency department visits, or hospital admissions)
- Whether additional opioid refills were prescribed after the initial postoperative prescription (this will also be evaluated through EMR queries)
- Evidence of opioid misuse (Current Opioid Misuse Measure-9 [COMM-9])

The one-time intervention for *surgeon* participants in the Intervention Arm will take place on approximately study day 97. This will entail procedure-specific direct feedback (through electronic communication) on patients’ opioid consumption-to-prescription ratio. E.g., “Your abdominal hysterectomy patients were prescribed a mean 60 opioid pills last month. These patients consumed a mean 20 pills (33%).” Surgeon participants who perform more than one of the specified procedures (see section 4.2, above) will receive nudging communications for each individual procedure. Since the data on opioid consumption provided to surgeons is based on self-report data from consented patients, surgeons will be specifically informed that the data is self-reported through inclusion of the following statement: “This is based off self-reported pill counts. The information is self-reported and not validated so it could be erroneous.”

Surgeon participants randomized to the Control Arm will not be contacted directly at any time during the study.

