#### 11.2.1 Treatment Assignment Procedures

For randomization, a list of all surgeon participants will be generated. Using random.org's sequence generator, a true random integer sequence derived from atmospheric noise will determine order in the list. Randomization will be stratified by surgical specialty (e.g., neurological surgery) and by mean opioid prescribing amount during the first 60-day surgical period prior to randomization (greater or equal to median vs. below median). We will at minimum ensure an even or near-even split among the four overall major surgical divisions (general, orthopedic, gynecologic, and neurological) across the intervention and control arms.

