## 11.5 Data Analyses

Primary feasibility and acceptability outcomes will be assessed on a descriptive basis among both the intervention and control surgeon groups (each group will be given a full explanation of the nature of the study following completion). After the intervention, we will also assess pre-post change in opioid prescription size (measured in oral morphine

equivalents) between the two groups. We will compare postoperative prescription size from the baseline (surgeries performed during days 1-60) to prescription size for surgeries performed during days 108-167. The specific exploratory outcome will be mean percentage change in procedure-specific prescription size. That is, mean size of post-intervention prescriptions (from electronic medical record queries) will be compared with mean pre-intervention prescription size by the same surgeon for the same procedure in order to calculate change from baseline. We will then compare mean per-surgeon percentage change in prescription size between the Intervention and Control Arms. We will plan a multiple regression analysis adjusting for case type and surgical specialty to further explore the targeted intervention effects.

To evaluate our other exploratory outcomes, we will assess pre-post changes across groups in patient opioid consumption, satisfaction with analgesia, medical visits for pain, opioid refills, and opioid misuse.

Additionally, we will examine differential consent rates between patients in the follow-up intervention patient group vs. those in the follow-up control patient group using descriptive statistics. This is due to the potential for varying consent rates among patients who are more or less satisfied with their postoperative analgesia following delivery of the one-time study intervention to surgeons.

We will not undersample or oversample surgeons who are women and/or members of minority racial and ethnic groups, so we expect to enroll them in proportion to their population prevalence at VUMC. We will use VUMC EMR data to assess sex/gender and race/ethnicity of patient participants, and will conduct analyses to investigate any differences between groups (including any sex/gender or race/ethnicity differences in willingness to participate in the study).

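### Randomization is stratified by baseline prescribing, but neither stated prescribing analysis adjusts for it: a small, avoidable loss of precision in an exploratory outcome

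*Combined protocol and SAP*

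**What the plan says.** On allocation, section 5 states: "Randomization will be stratified by both surgical specialty and by mean opioid prescription size during the initial block of surgeries". Section 11.2.1 repeats both factors and gives the form of the second, "by mean opioid prescribing amount during the first 60-day surgical period prior to randomization (greater or equal to median vs. below median"). It then adds: "We will at minimum ensure an even or near-even split among the four overall major surgical divisions".

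On analysis, section 11.5 defines the outcome as percentage change, within the same surgeon and procedure, from days 1-60 to days 108-167. Two analyses follow:

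- The arm comparison: "We will then compare mean per-surgeon percentage change in prescription size between the Intervention and Control Arms". No covariate is named, and the unit is the surgeon.
- The regression: "We will plan a multiple regression analysis adjusting for case type and surgical specialty to further explore the targeted intervention effects". Section 5 has a parallel sentence: "Multiple regression analyses adjusting for case type and surgical specialty will also be employed to permit more granular examination of the targeted changes". Neither says whether a row is a surgeon, a surgeon-by-procedure combination or a prescription.

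Section 7.1 provides for "Surgeon participants who perform more than one of the specified procedures", so some surgeons will have more than one case type.

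The prescribing outcome is exploratory. Section 11.2 expects up to 60 surgeons, justified by a rule of thumb of 12 per group, with no power calculation. Section 11.1 gives precise estimates of mean and variance, for planning a larger trial, as a chief interest.

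**The concern.** Specialty is carried from the randomization into the regression, but baseline prescribing is not. Baseline is used only as the reference value of the percentage change, which is not adjustment for it. Surgeons whose baseline mean is high by chance tend to show a fall, and those whose mean is low by chance a rise, so percentage change stays negatively related to baseline.

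Two consequences follow. First, a covariate that explains part of the outcome is left out, so precision can be lost. Second, stratifying on baseline removes some of the chance difference between arms, but an unadjusted standard error still counts that variation and so tends to be a little too large. Both bear on the quantities the pilot is meant to supply. The size depends on variances that the documents do not give.

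**Working it through.** **1. Factors side by side.** Randomization: specialty and baseline mean prescribing. Per-surgeon comparison: no covariate. Regression: case type and specialty. Baseline prescribing is the one stratification factor in neither analysis.

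**2. Plan figures.** 2 x 30 = 60 surgeons and 5 x 60 = 300 patients per phase, so 300 / 60 = 5 patients per surgeon per phase (60 is a ceiling). The lower case count used here is 3, from section 6.3: "Enrolled surgeons must complete a minimum 3 listed cases during the initial 60-day study period". There is no power-based figure to reproduce.

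**3. Why a change score leaves something to gain.** Let the baseline and follow-up means have equal variance and correlation rho. In units of that variance, a change score has variance 2(1 - rho) and a baseline-adjusted analysis 1 - rho^2. Their ratio is (1 + rho)/2.

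| rho | 2(1 - rho) | 1 - rho^2 | ratio |
|---|---|---|---|
| 0.3 | 1.4 | 0.91 | 0.65 |
| 0.5 | 1.0 | 0.75 | 0.75 |
| 0.7 | 0.6 | 0.51 | 0.85 |
| 0.9 | 0.2 | 0.19 | 0.95 |

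This ignores stratification, which already secures part of the gain. It shows the direction, not the size for this trial.

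**4. Simulation with stratification at the baseline median and no true effect.** Assumed: 60 surgeons, 5 prescriptions per surgeon per period, total log-SD 0.5, 1,500 runs per setting. The share is the between-surgeon part of the log variance. Standard errors are in percentage points.

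| share | change log-SD | unadjusted: reported / true SE | true SE with log baseline | information ratio |
|---|---|---|---|---|
| 0.2 | 0.1 | 8.55 / 8.08 = 1.06 | 7.71 | (8.08/7.71)^2 = 1.10 |
| 0.2 | 0.2 | 10.02 / 9.55 = 1.05 | 9.33 | (9.55/9.33)^2 = 1.05 |
| 0.4 | 0.1 | 7.35 / 7.10 = 1.04 | 6.95 | (7.10/6.95)^2 = 1.04 |
| 0.4 | 0.2 | 8.89 / 8.69 = 1.02 | 8.61 | (8.69/8.61)^2 = 1.02 |
| 0.6 | 0.1 | 6.06 / 6.19 = 0.98 | 6.17 | (6.19/6.17)^2 = 1.01 |
| 0.6 | 0.2 | 7.73 / 7.96 = 0.97 | 7.97 | (7.96/7.97)^2 = 1.00 |

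The correlation of percentage change with baseline was -0.16 to -0.43. Null rejection of the unadjusted comparison was 3.4%-5.7% at a nominal 5%. In the first row, adding only the median stratum brought the reported SE to 7.99 but left the true SE at 8.08. The continuous baseline is what adds precision.

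**5. Wider grid.** Four specialties by the median split, 60 surgeons, case log-SD 0.3-0.5, between-surgeon log-SD 0.2-0.4, and 3 or 5 cases in each period. The comparison is a specialty-adjusted regression of percentage change with and without log baseline.

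- Surgeon-change log-SD 0.10: information ratio about 1.01-1.21; unadjusted SE 0-10% too large.
- Surgeon-change log-SD 0.20-0.30: about 0.99-1.19; unadjusted SE at most about 8% too large.

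Monte Carlo error is about 0.02, so ratios near 1 cannot be told from no gain.

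**6. The unstated unit.** If rows were prescriptions treated as independent, the design effect with 5 per surgeon is 1 + (5 - 1) x ICC. For assumed ICCs of 0.1, 0.3 and 0.5 that is 1.4, 2.2 and 3.0. In the step 4 settings such an analysis rejected a true null 11.5%-22.3% of the time. This applies only if the regression is run that way.

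**The case against.** The stakes are low. The primary outcomes are descriptive. The regression is a further look at an exploratory result, with no significance threshold or power target. Baseline already serves as the within-surgeon, within-procedure reference. Null rejection of the unadjusted comparison is near nominal, and any error in its SE is mostly on the conservative side. The gain also depends on how much surgeons' changes vary, which nobody knows before the trial. All of this stands and keeps the point minor. It does not remove it, because the covariate is already collected and the pilot wants precision.

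The simulations also leave out case type and multi-procedure surgeons, so they approximate the planned regression. That stands too.

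A reader might infer more from two places in the plan:

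- **That only the specialty split will be achieved.** The sentence in section 11.2.1 on a minimum split could be read this way, and the gain would then be larger. But sections 5 and 11.2.1 both state that baseline prescribing is a stratification factor, and nothing says it will be dropped.
- **That far more cases will be counted at follow-up than at baseline.** Baseline prescribing is counted for patients who consent and complete the pill count (section 8.2.2), follow-up at screening (section 8.2.4). With 3 against 10 cases the ratio reached 1.46, but only at surgeon-change log-SD 0.10 and with 3/10 = 30% consent and completion. The consent goal in section 11.4.1 is above 50%.

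**Conclusion.** The point holds as a minor one. Baseline prescribing is a stratification factor and is adjusted for in neither stated prescribing analysis. With stratification achieved, 60 surgeons, equal counts of 3 or 5 cases per period and the assumed SDs, adding log baseline yields about 1.0-1.2 times the information, and the unadjusted SE is about 0-10% too large. Both shrink toward nothing as the surgeon-change SD rises.

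Three stronger conclusions are not supported:

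- The arm comparison is not materially biased by the omission, and the primary outcomes are unaffected.
- A later trial would not necessarily be oversized. That would require it to be sized on the unadjusted variance and then to stratify the same way and use an analysis that recovers the gain.
- The plan does not commit to an analysis that ignores clustering. The regression's unit is missing detail. The per-surgeon comparison already has the surgeon as its unit.

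Nor would the covariate remove the upward pull on each arm's mean percentage change that comes from dividing by a mean of few cases. That is a separate property of the chosen outcome.

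**What to change.** In section 11.5, keep percentage change as the named outcome and add the continuous log of baseline mean prescription size to the regression, alongside case type and specialty. State the unit in the same place:

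- **One row per surgeon:** use the surgeon's overall baseline mean or a baseline weighted by procedure mix, and say how case type is coded for a surgeon with several procedures.
- **Rows per surgeon-by-procedure or per prescription:** use the same-procedure baseline, with a surgeon random intercept or small-sample cluster-robust errors. Treating such rows as independent would make the standard errors too small.

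A log-scale sensitivity analysis is optional. Section 5 should carry the same covariate list. The cost is a few sentences and one model degree of freedom. No further data, patients or surgeons are needed.

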## **1.5 Sample Size and Population**

**Patients (initial phase):** We anticipate successfully contacting 5 patients per day for a total of 300 patients.

**Surgeons:** We anticipate obtaining mean pre-post prescribing change in up to 60 surgeons (30 per group).

**Patients (second phase):** We anticipate successfully contacting 5 patients per day for a total of 300 patients.

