## 6.2 Exclusion Criteria

There are no planned exclusion criteria for study *surgeon* participants, although those performing <3 of the specified surgeries during the first 60-day period of surgeries will not be eligible for randomization.

Study *patient* candidates meeting any of the following exclusion criteria at baseline will be excluded from study participation:

- Opioid prescription filled (per VUMC electronic medical record [EMR] and patient self-report) between 3 months and 14 days prior to surgery
- Primary reason for surgery as assessed by chart review is cancer-related

- Surgery is a repeat/revision surgery (e.g., revision total knee arthroplasty)
- Patient has been inpatient for >3 days postoperatively prior to receiving post-discharge prescription
- Vulnerable populations: current pregnancy, prisoners
- Inability or unwillingness of patient to give informed consent
- (Partial exclusion) Prior participation in this study (e.g., a patient included in the initial patient group undergoing a left total knee arthroplasty on study day 15, followed by a right total knee arthroplasty on day 115; such a patient would be included in the initial patient group but would not be recontacted for the follow-up patient group)

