### 8.2.4 Follow-Up Patient Group Contacts and Surgeon Post-Intervention Prescribing Evaluation (Days 108-181)

#### Screening of Patient Candidates (EMR/PDMP) – Follow-Up Patient Group

- Age  $\geq 18$  years
- Undergoing specified surgeries with surgeon participants between study days 4108-167
- Provided opioid prescription that was subsequently filled
- Opioid-naïve (no prior opioid prescriptions between 14 and 90 days prior to the date of surgery)
- Non-cancer surgery
- Non-repeat/revision surgery
- Not a prior participant in the Initial Patient Group of this study
- Demographic information, including gender and race/ethnicity, will be collected
- Screening date will be recorded in the password-protected and encrypted research database

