## 11 STATISTICAL CONSIDERATIONS

### 11.1 General Design Issues

This is a pilot randomized controlled trial assessing the effect of a brief behavioral nudging intervention on surgeons' postoperative opioid prescribing. In addition to determining feasibility and acceptability, we are chiefly interested in obtaining precise estimates of mean and variance to aid in planning a larger, sufficiently powered efficacy trial.

Exploratory hypotheses include that (1) surgeons in the Intervention Arm will exhibit a larger pre-post percentage change in procedure-specific prescription size (measured by oral morphine equivalents [OMEs]) compared with surgeons in the Control Arm who do not receive the nudging intervention and (2) there will be no pre-post difference between the Intervention and Control Arms in terms of patient opioid consumption, opioid refills, medical visits for pain, satisfaction with analgesia, and opioid misuse.

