### 11.2 Sample Size and Randomization

We anticipate obtaining mean pre-post prescribing change in up to 60 surgeons (30 per group). This exceeds the suggested rule-of-thumb threshold of 12 per group for an adequately precise estimate of the variance of a continuous variable to use in future studies.(16)

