### 11.4.2 Exploratory outcomes

- Mean pre-post percentage change in procedure-specific prescription size, as measured by OMEs. Mean size of post-intervention prescriptions (from electronic medical record queries) will be compared with mean pre-intervention prescription size by the same surgeon for the same procedure in order to calculate change from baseline.
- Pre-post change in patient opioid consumption, as measured by OMEs
- Pre-post change in satisfaction with overall postoperative analgesia, as measured by patient-reported numeric rating scale
- Pre-post change in patient satisfaction with general amount of opioids prescribed
- Pre-post change in incidence of medical visits for pain (office visits, emergency department visits, and/or hospital admissions)
- Pre-post change in number of subsequent opioid refills after the initial postoperative prescription (from EMR/PDMP data)
- Surgeon-reported perceived usefulness of intervention (goal: median response to question “Do you think the nudge intervention would be useful?”  $\geq 4$  on 0-5 scale, where 0 is “not at all” and 5 “extremely.”)

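### Patient outcomes are compared as pre-post changes although the two phases contain different patients; adjusting for the surgeon's baseline mean would be more precise at no cost in data

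*Combined protocol and SAP*

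**What the plan says.** Section 11.4.2 defines the patient outcomes themselves as changes, for example "Pre-post change in patient opioid consumption, as measured by OMEs". Pain visits, refills and satisfaction are treated the same way. Misuse is missing from that list, but sections 1.3, 11.1 and 11.5 include it with the others. The hypothesis in section 11.1 is also framed as a change: "there will be no pre-post difference between the Intervention and Control Arms in terms of patient opioid consumption" and the remaining patient outcomes. The analysis sentence in section 11.5 is "we will assess pre-post changes across groups in patient opioid consumption, satisfaction with analgesia, medical visits for pain, opioid refills, and opioid misuse".

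The patients in the two phases are not the same people. Section 8.2.4 requires of each follow-up candidate: "Not a prior participant in the Initial Patient Group of this study". Section 6.2 gives the example of a patient with a second operation who "would not be recontacted for the follow-up patient group".

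Surgeons are randomised 1:1 after the initial phase, stratified by specialty and by baseline prescription size (section 11.2.1). For each phase, section 1.5 states: "We anticipate successfully contacting 5 patients per day for a total of 300 patients". Section 11.2 expects at most 60 surgeons, 30 per arm. The only regression in section 11.5 adjusts for case type and specialty. It appears with the prescription-size outcome and has no baseline value as a covariate.

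**The concern.** A change score helps when the baseline strongly predicts the follow-up value, as it may when the same person is measured twice. Here the link between phases runs only through the surgeon. If patients of the same surgeon resemble each other only weakly, the mean of a handful of initial-phase patients says little about that surgeon's follow-up patients. Subtracting it then removes little surgeon variation and adds the full sampling error of the baseline mean. Regression on the baseline mean uses the same data but gives that mean only the weight it deserves.

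Two features of the plan make this worth settling. Section 11.1 says that, beyond feasibility and acceptability, the main interest is in estimates precise enough to plan a larger trial. The hypothesis for the patient outcomes is that the arms do not differ, so avoidable noise makes a real difference easier to miss.

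**Working it through.** **Inputs from the plan.** 5 patients per day × 60 days = 300 patients per phase, and 2 × 30 = 60 surgeons; both stated totals reproduce. Patients per surgeon per phase: m = 300/60 = 5. Sixty is a ceiling. If 300 patients are still reached with 30 surgeons, m = 10.

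**Assumptions, not in the plan.** The ICC (the share of outcome variance lying between surgeons) is taken as 0.02 to 0.20. Surgeon effects are stable between phases, cluster sizes are equal, V (the variance of a surgeon mean) is the same in both phases, and surgeon means are analysed linearly.

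**Formulas.** The correlation between a surgeon's initial and follow-up means, from different patients, is r = m·ICC / (1 + (m − 1)·ICC). The variances per surgeon are:

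- follow-up mean alone: V
- change score: 2(1 − r)V
- follow-up mean adjusted for the baseline mean: (1 − r²)V

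Change score against adjustment: 2(1 − r)/(1 − r²) = 2/(1 + r), which exceeds 1 for every r below 1. Change score against follow-up only: 2(1 − r), which exceeds 1 only when r < 0.5. Setting r = 0.5 gives ICC = 1/(m + 1).

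**Example, m = 5, ICC 0.05.** r = 0.25/1.20 = 0.208. Against adjustment: 2/1.208 = 1.66. Against follow-up only: 2 × 0.792 = 1.58.

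| m | ICC | r | Change / adjusted | Change / follow-up only |
|---|---|---|---|---|
| 5 | 0.02 | 0.093 | 1.83 | 1.81 |
| 5 | 0.05 | 0.208 | 1.66 | 1.58 |
| 5 | 0.10 | 0.357 | 1.47 | 1.29 |
| 5 | 0.20 | 0.556 | 1.29 | 0.89 |
| 10 | 0.02 | 0.169 | 1.71 | 1.66 |
| 10 | 0.05 | 0.345 | 1.49 | 1.31 |
| 10 | 0.10 | 0.526 | 1.31 | 0.95 |
| 10 | 0.20 | 0.714 | 1.17 | 0.57 |

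At m = 5 the standard error is larger than with adjustment by √1.83 = 1.35 at ICC 0.02 and √1.29 = 1.13 at ICC 0.20. The change score breaks even with follow-up only at ICC 1/6 ≈ 0.17 for m = 5 and at 1/11 ≈ 0.09 for m = 10.

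**Sensitivity, m = 5, against adjustment.** If surgeon effects correlate at 0.8 between phases rather than 1, the range for ICC 0.02 to 0.20 is +86% to +38%. A simulation with 60 surgeons gave +80%, +64%, +46% and +25% at ICC 0.02, 0.05, 0.10 and 0.20, within about 4 points of the formula. With unequal patient numbers per surgeon it gave +90%, +69%, +58% and +36%.

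**The case against.** The strongest objection is that section 11.5 fixes no estimator for the patient outcomes. The per-surgeon change calculation is spelled out for prescription size only, and a model using both phases would fit the wording. That stands: baseline adjustment is unspecified, not excluded. But the outcomes are defined as changes and no baseline covariate is named, so subtraction is the natural reading.

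A reader might also infer more than the documents support:

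- *A fixed penalty.* The plan gives no ICC, and 60 surgeons is an upper limit. Any percentage depends on the ICC, the patients per surgeon and the comparator.
- *That subtraction is worse than ignoring baseline.* This holds only below the break-even ICC. The listed procedures run from tension-free vaginal tape to knee arthroplasty, so the unadjusted surgeon ICC for opioid consumption could lie above it. Adjusting for case type would lower the residual ICC. Neither direction can be asserted.
- *That randomisation alone makes the follow-up comparison unbiased.* Patients consent about 14 days after surgery, and section 11.5 itself anticipates that consent may differ between arms. Neither a change score nor baseline adjustment removes that.
- *That the check on patient harm rests on this contrast.* Sections 6.3 and 9.3 provide separate record reviews for pain problems, and section 9.2 has staff watch for arm differences in pain-related visits. None of these is described as a pre-post contrast.

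Finally, the formula is for linear analysis of surgeon means. Visits are an incidence, refills a count, and the rating of opioid amount has three categories, so the percentages are only a guide for those outcomes.

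**Conclusion.** The concern holds as a point about precision. With different patients in each phase, a simple change score is less precise than adjusting for the surgeon's baseline mean at any correlation below 1, under equal variances and apart from the small cost of estimating the slope. The size is conditional. For an assumed ICC of 0.02 to 0.20, stable surgeon effects and a linear surgeon-mean analysis, the excess variance is about 83% to 29% at 5 patients per surgeon and about 71% to 17% at 10. The ranking against follow-up only depends on the unknown ICC. No bias is shown, the outcomes are exploratory in a pilot without a power claim, and the feasibility and acceptability endpoints are untouched. It is still worth changing: the gain costs nothing and serves the aim stated in section 11.1.

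**What to change.** In sections 11.4.2 and 11.5, define each patient-outcome contrast as the between-arm difference in the follow-up group. Adjust it for the surgeon's initial-phase mean of the same outcome and for the stratification factors (specialty and baseline prescription-size stratum). Use a model suited to the outcome type, with surgeon kept as the randomised unit, for instance through a surgeon random effect. A constrained-baseline model that uses patients from both phases is an acceptable alternative. It also accommodates surgeons with few or no consenting initial-phase patients, since section 6.3 sets its minimum of 3 in cases, not in consenting patients.

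Report pre-post change descriptively only, together with the estimated ICC and the between-period correlation of surgeon effects, which the larger trial will need. Align the hypothesis in section 11.1 with this contrast. The cost is wording in the analysis plan; every value needed is already collected.
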